electrocardiogram (ECG); routine laboratory evaluations (hematology, serum chemistry, and urinalysis); assessment of protocol-related adverse events (AEs) and serious adverse events (SAEs); notation of concomitant medications; and disease evaluations (including computed tomography [CT] or magnetic resonance imaging [MRI] scans, Karnofsky performance status [KPS]).

For subjects enrolled on the dose-escalation phase of the study, the following specimens will be collected:

- archived tumor biopsies (optional)
- biopsies obtained during procedures conducted in the course of routine patient care (optional)
- circulating tumor cells
- whole blood RNA

For subjects enrolled on the dose-expansion phase of the study, the following specimens will be collected:

- biopsies of bladder cancers and/or bladder cancer metastatic deposits (eg, in patients without bladders using image-guidance as needed) will be required from all subjects before and after treatment with study drug. Samples will be collected at two timepoints: prior to the first treatment of Cycle 1, and after the last dose of Cycle 1 but prior to administration of the first dose of Cycle 2.
- archived tumor biopsies (optional)
- biopsies obtained during procedures conducted in the course of routine patient care (optional)
- exfoliated cells from voided urine or catheterized urine, and when available (in the case of patients with bladders who may be undergoing cystoscopic procedures) from bladder washings
- circulating tumor cells
- whole blood RNA

For subjects enrolled on either the escalation or expansion phase of the study, the following biomarker studies will be performed:

- PK evaluations (MEDI-573 serum concentrations) and IM evaluation (anti-MEDI-573 antibodies)
- pharmacodynamic evaluations, including

- analysis of circulating levels of IGF-1, IGF-2 and IGFBPs in blood and, for subjects in the dose-expansion phase, urine and
- analysis of exfoliated cells collected from voided urine, catheterized urine, and/or in the case of patients with bladders who may be undergoing cystoscopic procedures, bladder washings
- blood biomarker analysis
- whole blood RNA analysis

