For subjects enrolled on the dose-expansion phase of the study, the following specimens will be collected:

- biopsies of bladder cancers and/or bladder cancer metastatic deposits (eg, in patients without bladders using image-guidance as needed) will be required from all subjects before and after treatment with study drug. Samples will be collected at two timepoints: prior to the first treatment of Cycle 1, and after the last dose of Cycle 1 but prior to administration of the first dose of Cycle 2.
- archived tumor biopsies (optional)
- biopsies obtained during procedures conducted in the course of routine patient care (optional)
- exfoliated cells from voided urine, catheterized urine, and/or (in the case of patients with bladders who may be undergoing cystoscopic procedures) bladder washings
- circulating tumor cells
- whole blood RNA

For subjects enrolled on either the escalation or expansion phase of the study, the following biomarker studies will be performed:

- PK evaluations (MEDI-573 serum concentrations) and IM evaluation (anti-MEDI-573 antibodies)
- pharmacodynamic evaluations (including analysis of circulating levels of IGF-1, IGF-2 and IGFbps in blood and [for subjects in the dose-expansion phase] urine as well as exfoliated cells collected in voided urine, catheterized urine, or bladder washings)
- blood biomarker analysis
- whole blood RNA analysis

Treatment-emergent AEs and SAEs will be assessed from the time the subject receives the investigational product through 30 days after the last dose of MEDI-573. Adverse events will be graded according to the National Cancer Institute Common Terminology Criteria for Adverse Events Version 3.0 (NCI CTCAE V3.0). In addition, disease evaluations (including CT or MRI scans, physical examination, and KPS) will be performed after every 2 cycles of treatment until documentation of disease progression or initiation of alternative anticancer therapy. For subjects who discontinue treatment due to reasons other than disease progression or initiation of alternative anticancer therapy, disease evaluations will be performed every 3 months until documentation of disease progression, initiation of alternative anticancer therapy, or the end of study (defined as 1 year after the last subject entered the study).

A study flow diagram is presented in [Figure 2.4-1](#).

[figure not shown]

Figure 2.4-1 Study Flow Diagram

3 Study Procedures

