- 10) Women of non-child-bearing potential (defined as being >1 year post-menopausal or surgically sterile) or using effective contraception, eg, use of oral contraceptives with an additional barrier method (since the investigational product may impair the effectiveness of oral contraceptives), double barrier methods (diaphragm with spermicidal gel or condoms with contraceptive foam), Depo-Provera, partner vasectomy, or total abstinence, from the time the informed consent is signed through 30 days after the last dose of MEDI-573. Male subjects with partners of child-bearing potential must be surgically sterile or use contraceptive method as described above from the time of the initiation of MEDI-573 through 30 days after the last dose of MEDI-573.
- 11) Subjects in the dose-expansion cohorts must have at least one lesion that is measurable using RECIST. Other non-measurable lesions are allowed.

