3.7.4 Disease Evaluations

Tumor measurements and assessments will be based on RECIST (Therasse et al, 2000) and will be performed as specified in [Table 3.6-1](#) and [Table 3.6-2](#) (Schedule of Subject Evaluations: Screening and Treatment Periods) and [Table 3.6-3](#) (Schedule of Subject Evaluations: Follow-up Periods). Additional tumor measurements may be performed at the discretion of the investigator or according to institutional practice. In subjects who achieve a complete or PR to treatment, tumor measurements will be repeated at least 4 weeks later using the same imaging tests. The same tumor assessment method should be used throughout the treatment period.

Tumor measurements must be recorded in metric notation by use of a ruler or calipers, and the same method/technique of tumor assessment must be used throughout the study. Whenever possible, tumor measurements will be conducted by the same person for a given subject. Imaging based evaluation is preferred to evaluation by clinical examination when both methods have been used to assess the antitumor effect of the treatment. The analysis for tumor response will be based on the investigator's assessment during the conduct of the study. Radiographic images may be collected and archived by the Sponsor or its designee.

Tumor assessments may include the following evaluations: physical examination, chest radiograph (x-ray), CT or MRI scan of the chest, abdomen, and pelvis, and CT scan or MRI of the brain. CT scan or MRI of the brain will be performed if the subject is neurologically symptomatic. The same method must be used for all subsequent tumor assessments. Bladder tissue and/or bladder cancer tissue obtained via cystoscopic biopsy, transurethral resection of bladder tumor (TURBT) or other surgical removal may also be acquired in the course of routine subject care, if the subject consents.

- Lesions detected by physical examination will only be considered measurable if superficial, eg, skin nodules and palpable lymph nodes. Documentation by color photography including ruler is recommended for estimating the size of skin lesions.

- Chest x-ray. Lesions considered acceptable for measurement on chest radiograph should be clearly defined and surrounded by aerated lung. However, CT is preferable.

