- CT scans of the chest, abdomen, and pelvis. CT should be performed with contiguous cuts in slice thickness of 10 mm or less. Spiral CT should be performed using a 5-mm contiguous reconstruction algorithm.
- MRI scans. MRI is acceptable for measurement of lesions provided that the same anatomical plane is used for serial assessments. If possible, the same imaging device should be used for serial evaluations. In case of MRI, measurements will be preferably performed in the axial (transverse) plane on contrast enhanced T1 weighted images. However, there are no specific sequence recommendations.

Measurability of Tumor Lesions at Screening

At Screening, tumor lesions will be categorized as follows:

- **Measurable Lesions** - Measurable lesions are defined as those that can be accurately measured in at least one dimension (longest diameter to be recorded) as ≥ 20 mm with conventional techniques (CT, MRI, x-ray) or as ≥ 10 mm with spiral CT scan. All tumor measurements must be recorded in millimeters by use of a ruler or calipers.
- **Nonmeasurable Lesions** - Nonmeasurable lesions are defined as all other lesions (or sites of disease), including small lesions (longest diameter < 20 mm with conventional techniques or < 10 mm using spiral CT scan). Lesions considered truly nonmeasurable include the following: bone lesions, leptomeningeal disease, ascites, pleural/pericardial effusion, inflammatory breast disease, lymphangitis cutis/pulmonis, abdominal masses that are not confined and followed by imaging techniques, and cystic lesions.
- **Target Lesions** - All measurable lesions up to a maximum of 5 lesions per organ and 10 lesions in total, representative of all involved organs, should be identified as target lesions and recorded at Screening. Target lesions should be selected on the basis of their size (those with the longest diameter) and their suitability for accurate repeated measurements (either by imaging techniques or clinically). A sum of the longest diameter (LD) for all target lesions will be calculated and reported as the baseline sum LD. The baseline sum LD will be used as the reference by which to characterize the objective tumor response.
- **Non-Target Lesions** - All other lesions (or sites of disease) should be identified as non-target lesions and should also be recorded at Screening. Measurements of these lesions are not required, but the presence or absence of each should be noted throughout the study.

Response Criteria

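### Section 3.7.4 does not keep biopsied or resected lesions out of the target sum, so tissue removal in the expansion phase can be scored as response

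*Protocol*

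**What the plan says.** **Target selection and scoring.** Under Target Lesions, Section 3.7.4 of the protocol says that "All measurable lesions up to a maximum of 5 lesions per organ and 10 lesions in total" should be recorded as targets at Screening. They are to be chosen by size and by "their suitability for accurate repeated measurements (either by imaging techniques or clinically". All remaining lesions are non-target. Target CR is the disappearance of every target. PR is a fall of at least 30% from baseline in the sum of longest diameters (LD). Neither definition asks why a lesion became smaller.

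**Tissue sampling.** For the expansion phase, Section 2.4 states that "biopsies of bladder cancers and/or bladder cancer metastatic deposits" "will be required from all subjects before and after treatment with study drug". The two samples are taken "prior to the first treatment of Cycle 1, and after the last dose of Cycle 1" and before Cycle 2 starts. Refusal is an exclusion (Section 3.1.2, item 19). Section 3.7.4 adds that bladder or bladder-cancer tissue "obtained via cystoscopic biopsy, transurethral resection of bladder tumor (TURBT) or other surgical removal may also be acquired" in routine care, with consent.

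**Entry and timing.** Section 3.1.1, item 11: "Subjects in the dose-expansion cohorts must have at least one lesion that is measurable using RECIST". Table 3.6-1 lists the baseline CT or MRI and the first biopsy both under Screening and does not order them. On-treatment scans fall every two cycles, the first within the 3 days before Cycle 3 (Section 3.6).

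**Endpoint.** Section 5.4.4 defines ORR as the proportion of subjects with CR or PR confirmed at least 4 weeks later. Response is the investigator's assessment (Section 3.7.4).

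**The concern.** Determining tumor response is a stated aim of the expansion phase (Section 2.4). The same phase obliges every subject to have tumor tissue taken twice before response is first measured on treatment, and it foresees surgical removal as well. Nothing in Section 3.7.4 reserves a non-target lesion for sampling, removes a resected lesion from the sum, or makes response not evaluable after a resection.

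If a target is cut down or removed, the loss of tissue enters the sum LD as if the drug had caused it. Section 5.4.3 then relates changes in tumor tissue to clinical activity, so one procedure can feed both sides of that correlation.

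An analysis plan written later could not fully repair this, because sites choose the targets and order the scans at Screening.

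**Working it through.** **Plan's own figure.** Two cohorts of about 10 (Section 5.1) give 2 × 10 = 20, as Section 2.4 states. There is no target ORR, alpha or power to reproduce.

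**Timing, with 21-day cycles and no delay.** The second biopsy lies after the Day 15 dose and before Day 22, so on Days 15 to 21. Cycle 3 starts on Day 43, so the first scheduled on-treatment scan is on Days 40 to 42. Both biopsies precede it. The first biopsy may come before or after the baseline scan. If it comes before, its effect is already in the baseline sum.

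**Complete removal of one of k equal targets.** The fall in sum LD is 1/k, against a PR threshold of 30%.

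| k | Fall in sum LD | Reaches |
|---|---|---|
| 1 | 100% | target CR |
| 2 | 50% | PR |
| 3 | 33.3% | PR |
| 4 | 25% | neither |

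With unequal lesions, PR is reached if the removed lesion held at least 30% of the baseline sum.

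**Partial removal of a sole target.** The loss needed is 0.30 × LD. At the measurability limits in Section 3.7.4 this is 3 mm for a 10 mm lesion (spiral CT) and 6 mm for a 20 mm lesion (conventional techniques). For an illustrative 30 mm lesion it is 9 mm.

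**From target response to overall response (Table 3.7.4-1).** There must be no new lesion and no non-target progression. Target CR becomes overall CR if non-target disease is absent or also in CR. If non-target lesions persist without progressing, it becomes PR. Either counts in ORR. The repeat scan at 4 weeks or later does not screen this out, because a resected lesion stays absent.

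**Effect on ORR, taking all subjects in a cohort as denominator (exact 95% intervals).**
- Cohort of 10: one such response gives 1/10 = 10% (0.3 to 44.5), against 0/10 = 0% (0 to 30.8).
- Both cohorts: 1/20 = 5% (0.1 to 24.9), against 0/20 = 0% (0 to 16.8).

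**Frequency.** The protocol gives none. If each subject had an assumed chance p of such a response, the chance of at least one among n is 1 − (1 − p)^n. For p = 5%, 10% and 20% this is 40%, 65% and 89% with n = 10, and 64%, 88% and 99% with n = 20. These values of p are illustrations only.

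**The case against.** Several stronger readings are tempting, and the text does not bear them out.

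- A reader might infer that the rules compel a biopsied lesion to be a target. They do not: the lesion must be measurable and within the caps, the verb is should, and the suitability criterion lets an investigator pass over a lesion due for excision. That criterion does not mention biopsy, however, and it offers little help when the lesion is the subject's only measurable one.
- A reader might infer that the same lesion is sampled twice before any scan. The protocol requires neither the same lesion nor a measurable one, and the first scan is the screening scan.
- A reader might infer that the mandatory biopsy itself commonly produces a PR. The protocol does not say how much tissue is taken, and a needle sample would seldom cut LD by 30%. The material risk lies in TURBT, excision or sampling of a small lesion. TURBT and surgical removal appear as routine care, not as study procedures.

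It can also be said that a therapeutic resection might count as alternative anticancer therapy, at which disease evaluations stop (Section 2.4). The protocol does not say whether it does. The censoring in Section 5.4.4 for such therapy covers duration of response, time to progression and PFS, not ORR.

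Finally, ORR is a descriptive secondary measure without a threshold, and continuation of the expansion rests on tissue pharmacodynamics (Section 4.9). That stands, and it limits the consequence. It does not close the gap.

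**Conclusion.** The concern holds in a limited form: as written, Section 3.7.4 allows tissue removal to be scored as CR or PR in the expansion phase, and neither the response table nor the confirmation scan prevents it.

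The size is 10 percentage points of ORR per affected subject in a cohort of 10, or 5 points over 20. This assumes that the removed lesion was a target carrying at least 30% of the baseline sum, that it was lost after the baseline scan, and that there was no new lesion or non-target progression through confirmation. How many subjects this would affect cannot be derived from the protocol, so a reader should not infer a total bias of, say, 10 to 30 points.

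The error can only raise apparent response. It affects how antitumor activity and its correlation with tissue markers are interpreted, and no trial decision depends on it. The change is worth making because it is cheap and because target choice and scan order cannot be reconstructed afterwards.

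**What to change.** Add to Section 3.7.4:

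1. A lesion planned for biopsy is recorded as non-target whenever another measurable lesion exists.
2. If it is the only measurable lesion, the baseline scan is scheduled after the pre-treatment biopsy, within the existing 28-day screening window.
3. If a target or non-target lesion is resected or excised after baseline, its response is entered as Unknown in Table 3.7.4-1 from that date, so that its removal cannot yield CR or PR. Progression still counts.
4. Subjects whose only target was biopsied after baseline are flagged, and ORR is reported with and without them as responders. This covers the second biopsy of a sole target, which item 2 cannot. The flag must be collected during the study; the reporting line can sit in the SAP.

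**Cost.** Amendment wording, one data flag and one extra line of output. Scan order needs planning at Screening, and a scan already done may have to be repeated. A few single-lesion subjects may become not evaluable for response. Because the table turns an Unknown in either category into an overall Unknown when nothing has progressed, a genuine PR could occasionally be lost after excision of another lesion. ORR may therefore be slightly lower. None of this changes who is biopsied, resected or treated.

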3.7.5 Pharmacokinetic and Immunologic Evaluations

Blood samples for assessment of PK parameters of MEDI-573 and anti-MEDI-573 antibodies will be collected as described in [Table 3.6-1](#), [Table 3.6-2](#), and [Table 3.6-3](#). At Cycle 1 Day 1, serum for PK analysis will be collected immediately prior to infusion, immediately following infusion, and for subjects in Cohorts 1 through 5 and the expansion phase only, PK samples will also be collected 2 and 6 hours post infusion. Subjects in Cohorts 6 and 7 will not have a 2 or 6-hour post infusion PK collection. Additional PK samples will be collected during Cycle 1 on Day 2 at 24 hours post Day 1 infusion \pm 2 hours and Day 3 at 48 hours post Day 1 infusion \pm 2 hours, Day 8 and Day 15 pre-infusion and immediately after the infusion. Subsequently PK samples will be collected pre-infusion and immediately following infusion (\pm 5 minutes) of MEDI-573 every 7 days (ie, on Days 1, 8, and 15 of each cycle, Cohorts 1 through 5 and dose expansion phase) or every 21 days (ie, on Day 1 of each cycle, Cohorts 6 and 7), at the time of discontinuation of MEDI-573, and at 21 days, 30 days and 3 months post-therapy. Samples for anti-MEDI-573 antibodies will be collected at Screening and subsequently prior to each infusion of MEDI-573.

Details for collection, aliquoting, storage, and shipment of plasma samples for PK and IM evaluations are presented in the Specimen Collection Manual provided by the Sponsor.

3.7.6 Pharmacodynamic Evaluations

3.7.6.1 Biomarker Analysis

Blood collection for assessment of biomarkers and other biological processes will be performed as described in [Table 3.6-1](#), [Table 3.6-2](#), and [Table 3.6-3](#).

Specific biomarkers may include free and bound IGF-1, IGF-2, and IGFBP levels, which will be evaluated by the Sponsor. Growth hormone, insulin, and tumor markers (when appropriate, such as prostate specific antigen [PSA] and cancer antigen 125 [CA 125]) will be drawn and evaluated at local clinical laboratories.

Details regarding blood sample collection for assessment of biomarkers are described in the Specimen Collection Manual provided by the Sponsor.

Growth hormone and insulin biomarkers will be collected at one timepoint per visit as described in [Table 3.6-1](#), [Table 3.6-2](#), and [Table 3.6-3](#). Tumor markers will be collected as clinically indicated. Samples for biomarker evaluations to be shipped to the sponsor will be collected at the following timepoints:

- Cycle 1 Day 1: pre-infusion
- Cycle 1 Day 1: end of infusion
- Cycle 1 Day 1: 2 hours post-infusion
- Cycle 1 Day 1; 6 hours post-infusion
- Cycle 1 Day 2: 24 hours post-Day 1 infusion
- Cycle 1 Day 3: 48 hours post-Day 1 infusion
- Cycle 1 Day 8: pre-infusion
- Cycle 1 Day 8: end of infusion
- Cycle 1 Day 15: pre-infusion
- Cycle 1 Day 15: end of infusion
- Cycle 2 and higher Days 1, 8 and 15: pre-infusion and end of infusion (Cohorts 1 through 5 and the expansion phase)
- Cycle 2 and higher Day 1 only (Cohorts 6 and 7)
- End of Treatment
- Day 21 post-therapy

- Day 30 post-therapy
- 3 months post-therapy

The levels of IGF-1 and IGF-2 suppression by MEDI-573 determined during dose-escalation will be used to determine the dose administered to subjects enrolled in the dose-expansion phase of the study. In the dose-expansion phase of the study, exfoliated cells from voided urine, catheterized urine, and/or (in the case of subjects with bladders who may be undergoing cystoscopic procedures) bladder washings will be taken at Screening, on Day 1 of Cycle 2 and every cycle thereafter, and the End of Treatment. Cells and proteins from voided urine will be obtained from urine samples collected at Screening, Days 1, 8, and 15 of Cycle 1, on Days 1 and 15 of Cycle 2 and every cycle thereafter, and the End of Treatment. An additional sample for exfoliated urothelial cells from bladder washes or urine will be collected after the last dose on Cycle 1 but prior to administration of the first dose on Cycle 2.

Circulating tumor cells will be taken at Screening, on Days 1 of Cycle 2 and every cycle thereafter, and the End of Treatment and will be analyzed by the Sponsor.

3.7.6.2 Whole Blood RNA Analysis

Whole blood samples will be used to analyze the effects of MEDI-573 on levels of mRNA genes. This analysis is performed using Affymetrix whole genome expression array and TaqMan-based assay on selected panel of genes. Details regarding blood sample collection for assessment of mRNA expression are described in the Specimen Collection Manual provided by the Sponsor. If applicable, a CAST assay will be performed to evaluate potential point mutations in the key genes downstream of IGF signaling pathway to evaluate their correlations with clinical activity of MEDI-573.

3.8 Completion of Study and Loss to Follow-up

Subjects alive at the end of the study will be considered to have completed the study if they were followed until the end of the study (defined as 1 year after the last subject entered the study). It should be specified on the source document whether or not the subject completed the study follow-up procedures through the end of the study.

Subjects will be considered lost-to-follow-up only if no contact has been established by the time the study is completed such that there is insufficient information to determine the subject's status. Investigators should document attempts to re-establish contact with missing

subjects throughout the study period. If contact with a missing subject is re-established, follow-up should resume according to the protocol.

4 Safety Assessment

